8.3 Ivermectin: Rescue Medication, Post-Study, Screening Failures

Ivermectin used as described in this section for rescue medication or post-study will be provided as a single oral administration at the approved dose of 150 μ g/kg bw and is not an IMP, i.e. will not be presented as over-encapsulated tablets.

When ivermectin is administered at a follow-up or early termination visit, it must be administered only after completion of the procedures scheduled at that visit, and after confirmation of last menstrual period and a negative pregnancy test. Ivermectin will be administered to subjects under fasting conditions.

Subjects who fail screening in the communities or at the investigational centre will be referred to the National Program PNLMTN-CTP for MDA with ivermectin.

8.3.1 Rescue Medication in Part 1

In Part 1, ivermectin will be administered as rescue medication at any time during the study, at the investigator's discretion, to subjects with clinically significant worsening of symptoms and/or signs related to onchocerciasis.

8.3.2 Rescue Medication in Part 2

In Part 2, ivermectin will be proposed as rescue medication to all subjects with clinically significant worsening of symptoms and/or signs related to onchocerciasis at any time during the study and/or to subjects with increased mean number of skin microfilariae at Month 18, compared to the mean number at Month 12.

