10.2 Analysis Sets

The analysis sets are:

- Intention-to-treat (ITT) population: all randomised subjects who received at least one dose of IMP.
- Primary population for Part 1 primary endpoint and Part 2 combination rule endpoint for Alternative Scenario: Per protocol (PP) for nodulectomy at 6 months (ND6M), i.e. all ITT subjects who had Month 6 nodulectomy with live female adult worms, who completed treatment and who did not take prohibited medication during the study (see Appendix 8 Sections II and IV).
- Primary population for Part 2 proportion of subjects with microfilaria depletion at Month 24 endpoint: PP population for microfilaria, defined as all subjects in the ITT population who had microfilaria-positive skin-snips at baseline, who completed treatment, had skin snips at Month 24 or received ivermectin rescue before Month 24, and who did not take prohibited medication during the study (see Appendix 8 Sections II and IV).
- Primary population for Part 2 secondary endpoints 2a: PP population for nodulectomy at 24 months (ND24M), i.e. all ITT subjects who had Month 24 nodulectomy with female adult worms, who completed treatment and who did not take prohibited medication during the study.
- Primary population for Part 2 secondary endpoints 2b: PP population for nodulectomy at 24 months (ND24M) with live female adult worms, i.e. all ITT subjects who had Month 24 nodulectomy with live female adult worms, who completed treatment and who did not take prohibited medication during the study.
- Safety population: all randomised subjects who received at least one dose of IMP.

Subjects who take prohibited medications that may have an impact on the study objectives (Appendix 8- sections II and IV) are excluded from the PP populations. Specifically subjects who take medications with an anti-filarial or anti-Wolbachia effect at any time during the study (Appendix 8-section II) or strong CYP3A inducers or dexamethasone during the treatment period that may lower ABBV-4083 or albendazole exposures (see Appendix 8 - Section IV) are excluded from the PP population.

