Completed treatment for Part 1 is defined as taking at least 6 out of 7 days of randomised ABBV-4083, ABBV-4083 + albendazole or albendazole alone (Arms A, C or E, respectively), 12 out of 14 days of randomised ABBV-4083 (Arm B) or 6 out of 7 days of randomised ABBV-4083 and all of 3 days of randomised albendazole (Arm D). The same definitions of treatment completion will be applied to the similar arms in Part 2, except that subjects must also be administered ivermectin or matching placebo at Month 6 to be considered as having completed treatment.

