10.4 Handling of Potential Intercurrent Events for the Primary and Key Secondary Endpoints

Subjects who do not complete the treatment as defined above will be excluded from the PP populations (but will be included in the ITT analyses). Subjects in Part 2 with evidence of reinfection will be included in all analyses as it is not possible to distinguish between reinfection and a failure in this study. However, in sensitivity analyses, those subjects will be excluded from efficacy analysis. Subjects in Part 2 who do not have skin snips at Month 24 will be excluded from the PP for microfilaria population, except those who received ivermectin rescue before Month 24. Any subject who received ivermectin rescue before Month 24 as allowed per protocol will be counted as a failure in both the PP and ITT analyses of the Part 2 primary and key secondary endpoints. Subjects who do not have nodulectomy data at Month 6 (for Part 1 and for Part 2 Alternate Scenario) or Month 24 (for Part 2) will be excluded from the PP for the ND6M or ND24M populations, respectively. Subjects who take prohibited medications (see Appendix 8-sections II and IV) will be excluded from the PP analyses; subjects who take medications with an anti-filarial or anti-Wolbachia effect at any time during the study (see Appendix 8 - Section II) will be counted as failures in the ITT analyses.

In the ITT analysis of the primary and key secondary endpoints, if the result is missing for the assessment, the assessment of that outcome will be a failure if the absence of data is due to administration of prohibited medication or withdrawal due to efficacy or safety issue. In the event of withdrawal of informed consent, subject lost to follow-up or withdrawal for a reason independent from the treatment (e.g. moving, lethal accident), multiple imputation will be used to impute the missing data.

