- 13. Ophthalmological examinations: full ophthalmological examination includes ocular symptoms, ocular examinations including ocular alignment, mobility and pupillary response, visual function (visual acuity, visual field, colour vision), retinal examination and fundus photography, slit lamp examination of anterior and posterior segments and intraocular pressure. Eye microfilarial count and data for clinical outcomes in the eye will be recorded during the ophthalmological examination.
- 14. Assessments for clinical outcomes (see Study Operations Manual for details) in the skin to be performed during physical examinations where the time-points coincide.
- 15. 12-lead ECGs will be recorded in triplicate with 1 minute between recordings at all time-points. ECGs will be performed 1-2 h after intake of the IMP. ECG at early termination is only applicable if early termination is before Month 3.
- 16. Blood and urine samples for clinical laboratory safety tests (haematology, biochemistry & urinalysis (plus urine microscopy where indicated if urinalysis is abnormal and clinically significant).
- 17. IMPs will be administered daily on site and IMPs dispensation will be done via the IRT system. Treatment duration and IMPs dispensation scheme will be confirmed before start of the Part 2, depending on the regimen selected.
- 18. Administration of ivermectin must be only after completion of the procedures scheduled at the visit (including nodulectomy where scheduled), and after a negative pregnancy test. Rescue medication (ivermectin) will be offered at the investigator discretion to administer if worsening symptoms and/or signs related to onchocerciasis at any time throughout the study and/or to patients with increased mean microfilaria in the skin at Month 18, compared to the Month 12 mean value.
- 19. AE collection from signature of Informed Consent onwards. AE monitoring will be performed as specified in Section 9.3.4 and will include scheduled questioning at the indicated time-points.
- 20. In the event of certain AEs considered to be associated with the IMP, additional examinations may be conducted in order to better interpret the AE, including safety laboratory, PK, ophthalmological, physical, neurological and parasitological (eye and skin) examinations.

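### Part 2 makes the Month 6 ivermectin/placebo capsule part of treatment completion for every per-protocol set: this can drop valid Month 6 nodule data and conflicts with counting early-rescued subjects as failures

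*Protocol*

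**What the plan says.** - **Completion.** Protocol 10.2 sets minimum dosing days by arm for Part 1 and reuses them in Part 2, "except that subjects must also be administered ivermectin or matching placebo at Month 6 to be considered as having completed treatment". It makes no distinction by endpoint.
- **Month 6 nodule set.** Protocol 10.2 has one such set (PP for ND6M): "Primary population for Part 1 primary endpoint and Part 2 combination rule endpoint for Alternative Scenario". Completed treatment is a condition of entry.
- **Microfilaria set.** For the Part 2 primary endpoint, protocol 10.2 takes subjects "who completed treatment, had skin snips at Month 24 or received ivermectin rescue before Month 24". Completion is a separate condition, in addition to having Month 24 snips or rescue.
- **Exclusion rule.** Protocol 10.4 opens with "Subjects who do not complete the treatment as defined above will be excluded from the PP populations".
- **Rescue rule.** Later in 10.4, any subject given permitted ivermectin rescue before Month 24 "will be counted as a failure in both the PP and ITT analyses of the Part 2 primary and key secondary endpoints".
- **When rescue may occur.** Protocol 8.3.2 provides for rescue in Part 2 "to all subjects with clinically significant worsening of symptoms and/or signs related to onchocerciasis at any time during the study", so also before Month 6.
- **SAP.** SAP 1.0 covers Part 1 only and leaves Part 2 to a separate SAP, so it does not settle either question.

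**The concern.** The combination rule asks whether the initial course of ABBV-4083 plus albendazole clears *Wolbachia* better than ABBV-4083 alone, read from nodules removed at Month 6. The Month 6 capsule belongs to a different question, the effect of ivermectin on later microfilariae. Making it a condition of the Month 6 set can discard valid data and applies a stricter completion rule in Part 2 than in Part 1 to results that are then combined.

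The second problem touches the primary population of the Part 2 primary endpoint. A subject rescued before Month 6 is, by the plan's own rule, a certain failure. If that subject also misses the capsule, one sentence removes the subject from the per-protocol set and another counts the subject in it as a failure. Whoever writes the Part 2 SAP could follow either, and the response rates would differ.

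**Working it through.** **1. Can the Month 6 exclusion occur?** Appendix 2, Table 8 schedules a pregnancy test and IMP at Month 6. Protocol 6.5.2 requires IMP to be discontinued after a positive pregnancy test or at the subject's request, and keeps such subjects in the study with continued assessments. A subject can thus have full initial dosing and a Month 6 nodule but no capsule. Protocol 10.2 then removes the subject; a Part 1 subject with the same dosing and nodule stays. This applies only in the Alternate Scenario, to subjects with more than one operable site.

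**2. Power of the combination rule.** Inputs from protocol 10.3: 25 per arm in Part 1; 34 (K+L) versus 17 (N2) in Part 2; 90% versus 70% of worms clear; ICC 0.01 and 0.54; the stated worm-count distributions; inverse normal combination at 2-sided 0.10. Method: 20,000 beta-binomial simulations, with an exchangeable GEE and robust variance standing in for alternating logistic regression. Success means significance in Part 1 alone or in the combined test.

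Plan's figures first: 97.3% (stated 96%) for K+L versus N2, and 96.5% (stated 95%) for M versus N2. The Part 1 comparison alone gives 84.3% (stated 81%), so the stand-in runs slightly high. With an assumed share of Part 2 nodulectomy subjects lost:

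| Lost | K+L vs N2 | Power |
|---|---|---|
| 0% | 34 vs 17 | 97.3% |
| 5% | 32 vs 16 | 96.9% |
| 10% | 31 vs 15 | 96.7% |
| 20% | 27 vs 14 | 96.4% |
| 30% | 24 vs 12 | 95.8% |

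One exclusion is 1/17 = 5.9% of N2 or 1/34 = 2.9% of K+L.

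**3. The two rules for an early-rescued subject without the capsule.**
- 10.2, completion: capsule not given, so not completed.
- 10.2, microfilaria set: completion required, so out.
- 10.4, first sentence: non-completers excluded, so out.
- 10.4, rescue sentence: a failure in the per-protocol analysis, so in.

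No order of precedence is given.

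**4. Size at Month 24.** Plan's figures first, from the two-proportion test with pooled variance at 2-sided 0.017: 62 versus 31 at 70% versus 30% gives 91.7% (stated 91%); 62 versus 62 at 90% versus 65% gives 83.9% (stated 84%).

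If a fraction r of an arm is rescued early and misses the capsule, all are failures. Dropping them changes the response rate from p to p/(1 − r) and n to n(1 − r). The values of r are assumptions; the documents give none. Differences use unrounded rates.

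| Scenario | r active / control | Rates after dropping | Difference | Power |
|---|---|---|---|---|
| Base | counted as failures | 70.0% vs 30.0% | 40.0 | 91.7% |
| Base | 2% / 5% | 71.4% vs 31.6% | 39.8 | 90.3% |
| Base | 5% / 10% | 73.7% vs 33.3% | 40.4 | 89.9% |
| Base | 5% / 15% | 73.7% vs 35.3% | 38.4 | 84.7% |
| Base | 10% / 10% | 77.8% vs 33.3% | 44.4 | 95.4% |
| Base | 15% / 5% | 82.4% vs 31.6% | 50.8 | 99.3% |
| Alternate | counted as failures | 90.0% vs 65.0% | 25.0 | 83.9% |
| Alternate | 2% / 5% | 91.8% vs 68.4% | 23.4 | 80.7% |
| Alternate | 5% / 15% | 94.7% vs 76.5% | 18.3 | 65.6% |

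The direction also depends on the scale: in the last row the difference falls, but the odds ratio rises from 4.85 to 5.54.

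**The case against.** Several points on the other side stand.

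- **Order of capsule and nodulectomy.** A reader might infer that entry to the Month 6 set depends on a dose given after the endpoint is measured. Table 8, footnote 18 does say "Administration of ivermectin must be only after completion of the procedures scheduled at the visit (including nodulectomy where scheduled", but it is attached to the rescue-medication row (Months 18, 24 and early termination). The blinded capsule is in the IMP row, under footnote 17. Footnote 23 puts nodulectomy after the visit's other procedures, and protocol 7.3.2.2 has IMP given in the morning. The order is not established. The point needs only that the capsule is a same-visit dose outside the regimen tested.
- **Validity of the combined test.** A reader might also infer that differing sets invalidate it. An inverse normal test combines stage-wise p-values and does not need identical analysis sets. The mismatch concerns what is estimated, not type I error.
- **Rarity.** The capsule is given under direct observation, rescue is not a listed reason for stopping IMP, and protocol 6.5.2 aims at completing the course. Exclusion criterion 5 also removes subjects who cannot avoid ivermectin for 6 months. An early-rescued subject may well take the capsule, stay in the set and count as a failure. With 2 such losses from an active arm and 3 from N1, the rates are 43.4/60 = 72.3% and 9.3/28 = 33.2%: a difference of 39.1 points instead of 40.0.
- **ITT.** The ITT analysis still counts rescued subjects as failures.
- **Uniform rule.** One completion rule for all per-protocol sets is a recognisable choice, since the capsule is a randomised IMP. That supports it for Month 24 endpoints, but not for a Month 6 endpoint testing the initial course.

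One could also read the rescue sentence in 10.4 as the more specific rule and let it govern. That is reasonable, but the protocol does not say so.

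**Conclusion.** The concern holds as a defect in the analysis definitions. Followed literally, the protocol drops valid Month 6 nodule data for want of a capsule that is not part of the comparison. It also gives two incompatible instructions for an early-rescued subject who misses the capsule.

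For the combination rule the cost is needless, possibly selective exclusion; power barely moves, 97.3% to 95.8% even at 30% loss. For the Month 24 endpoint the effect depends wholly on assumed rates. In the Base Scenario cases shown, the difference ranges from 38.4 to 50.8 points against 40.0. A reader might infer that the rule systematically flatters the active arms. The documents do not support that: they give no rate of early rescue or missed capsules, and the bias runs either way.

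**What to change.** Change analysis definitions only, in protocol 10.2 and 10.4, and carry the changes into the Part 2 SAP:

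1. For the Part 2 Month 6 nodule set, define completion by the initial ABBV-4083/albendazole course alone, as in Part 1. Keep the capsule condition for Month 24 sets only.
2. State that rescue-as-failure takes precedence over the completion exclusion in the microfilaria per-protocol set, whether or not the Month 6 capsule was taken.

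The documents should also state the order of the blinded capsule and nodulectomy at Month 6, since footnotes 17, 18 and 23 leave it open.

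The cost is about two sentences, with no change to treatment or sample size. Stated per-protocol response rates may be slightly less favourable, because certain failures stay in the denominator.

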10.3 Determination of Sample Size

10.3.1 Determination of Sample Size in Part 1

For the Part 1 primary hypothesis that compares the proportion of live female adult worms without *Wolbachia* at Month 6 between a single-drug ABBV-4083 arm (Arm A or Arm B) and the albendazole arm (Arm E), an alternating logistic regression will be used to compare the endpoint between two arms, taking into account the clustering of this worm-level endpoint by subject. Using simulations that add substantial clustering by subject to the endpoint values and assuming the number of worms in each subject varies from 1 to 10, ⁵⁴ following the multinomial distribution with probability = (0.20, 0.16, 0.16, 0.16, 0.08, 0.08, 0.08, 0.03, 0.03, 0.02) for values (1, 2, 3, 4, 5, 6, 7, 8, 9, 10), 17 subjects per arm will provide 88% power to detect the difference between a single-drug ABBV-4083 arm (Arm A or Arm B) where 70% of worms are without *Wolbachia* and the albendazole arm (Arm E) where 30% of worms are without *Wolbachia* (2-sided $\alpha = 0.10$). The clustering of the endpoint values by subject is provided by the Pearson intraclass correlation coefficient (ICC) for binary outcomes ⁸⁰ and was given as ICC = 0.54 for simulated arms where 70% or 30% of the worms are without *Wolbachia*.

For the Part 1 primary hypothesis that compares the proportion of live female adult worms without *Wolbachia* at Month 6 between the combination arm of ABBV-4083 + albendazole for 7 days (Arm C) and the single-drug ABBV-4083 arm (Arm A), 25 subjects per arm will provide 81% power to detect the difference between the combination arm where 90% of worms are without *Wolbachia* and the single-drug arm where 70% of worms are without *Wolbachia* (2-sided α =0.10 using alternating logistic regression). ICC = 0.54 was added to the simulated arm where 70% of the worms are without *Wolbachia*. Minimal clustering (ICC = 0.01) was added to the simulated arm where 90% of the worms are without *Wolbachia* because the difference between subjects would be negligible for such a high response rate. 30 subjects will be enrolled per arm to account for 17% drop out by Month 6.

10.3.2 Determination of Sample Size in Part 2

For the Part 2 primary hypothesis in the Base Scenario that compares the proportion of subjects without skin microfilariae at Month 24 between an active arm (Arm K, L or M) and the placebo arm (Arm N1), 62 subjects in the active arm and 31 subjects in the placebo arm will provide 91% power to detect the difference between an active arm (Arm K, L or M) where 70% of subjects are without skin microfilariae at Month 24 and the placebo arm (Arm N1) where 30% of subjects are without microfilariae at Month 24, using a logistic regression with 2-sided α =0.017. In addition, 62 subjects per arm will provide 80% power to detect the difference between two active arms where 90% and 70% of subjects are without skin microfilariae at Month 24, respectively, using a logistic regression with nominal 2-sided α =0.05. Assuming a 25% drop-out rate by Month 24, 84 subjects in each active arm and 42 subjects in the placebo arm are planned to be enrolled.

For the Part 2 primary hypothesis in the Alternate Scenario that compares the proportion of subjects without skin microfilariae at Month 24 between each active arm (Arm K, L or M) and the control arm (Arm N2: 7 days of ABBV-4083), 62 subjects per arm will provide 84% power to detect the difference between an active arm (Arm K, L or M) where 90% of subjects are without skin microfilariae at Month 24 and the control arm (Arm N2) where 65% of subjects are without microfilariae at Month 24, using a logistic regression with 2-sided α =0.017.

For the Part 2 combination rule hypothesis in the Alternate Scenario that compares the proportion of live female adult worms without Wolbachia at Month 6 between the combination arms of ABBV-4083 + albendazole for 7 days (Arm K plus Arm L) and the ABBV-4083 single drug arm (Arm N2), 17 subjects per each of Arms K and L for a total of 34 subjects in Part 2 in addition to the 25 subjects per arm in Part 1 will be able to provide an overall power of 96% to detect the difference between the combination arm where 90% of worms are without Wolbachia and the single drug arm where 70% of worms are without Wolbachia (2-sided α =0.10) in either Part 1 or Part 2, using an inverse normal combination test that combines the pvalues of alternating logistic regressions that use data from Part 1 only and Part 2 only. The assumption for the number of worms in each subject in Part 2 is adjusted to a multinomial distribution with probability = (0.22, 0.18, 0.17, 0.16, 0.08, 0.06, 0.06, 0.03, 0.02, 0.02) for values (1, 2, 3, 4, 5, 6, 7, 8, 9, 10) in order to account for the design that only worms from one nodule per subject in Part 2 will be used for this analysis. If Part 1 Arm B of ABBV-4083 for 14 days is used for Arms K and L of Part 2, Arm M would be the 4083/albendazole combination that is compared to Arm N2. 17 subjects in Arm M Part 2 in addition to the 25 subjects per arm in Part 1 will be able to provide an overall power of 95% using the same method. Assuming 17% of the subjects per arm drop out by Month 6, the enrolment in the alternate scenario will require at least 25% of subjects of those retained to Month 6 nodulectomy to have > 1 nodule site in the arms used to test this hypothesis to obtain the power shown above.

10.4 Handling of Potential Intercurrent Events for the Primary and Key Secondary Endpoints

Subjects who do not complete the treatment as defined above will be excluded from the PP populations (but will be included in the ITT analyses). Subjects in Part 2 with evidence of reinfection will be included in all analyses as it is not possible to distinguish between reinfection and a failure in this study. However, in sensitivity analyses, those subjects will be excluded from efficacy analysis. Subjects in Part 2 who do not have skin snips at Month 24 will be excluded from the PP for microfilaria population, except those who received ivermectin rescue before Month 24. Any subject who received ivermectin rescue before Month 24 as allowed per protocol will be counted as a failure in both the PP and ITT analyses of the Part 2 primary and key secondary endpoints. Subjects who do not have nodulectomy data at Month 6 (for Part 1 and for Part 2 Alternate Scenario) or Month 24 (for Part 2) will be excluded from the PP for the ND6M or ND24M populations, respectively. Subjects who take prohibited medications (see Appendix 8-sections II and IV) will be excluded from the PP analyses; subjects who take medications with an anti-filarial or anti-Wolbachia effect at any time during the study (see Appendix 8 - Section II) will be counted as failures in the ITT analyses.

In the ITT analysis of the primary and key secondary endpoints, if the result is missing for the assessment, the assessment of that outcome will be a failure if the absence of data is due to administration of prohibited medication or withdrawal due to efficacy or safety issue. In the event of withdrawal of informed consent, subject lost to follow-up or withdrawal for a reason independent from the treatment (e.g. moving, lethal accident), multiple imputation will be used to impute the missing data.

